## 2 RATIONALE FOR THE STUDY

The overall purpose of this study is to support the development of an oral formulation of BVD-523 for the treatment of patients with advanced cancers. BVD-523 is a highly potent, selective, and pharmacologically active inhibitor of ERK family kinases. The compound has demonstrated efficacy as a single agent in preclinical models of colon, pancreatic and melanoma cancers (Section 1.4.2), and has potential for application alone or in combination with existing cancer chemotherapeutics.

This first-in-human study is being performed to assess the safety and tolerability of BVD-523 given orally, twice daily for 21-day cycles. The pharmacokinetics and pharmacodynamics of BVD-523 will also be explored after the first doses administered on Day 1, at steady state on Day 15, at the end of the first cycle of treatment (Day 22), and as indicated after completion of Cycle 1. Pharmacokinetic, pharmacodynamics, and/or Holter measurements may be suspended pending review of accumulated patient experience.

### 2.1 RATIONALE FOR THE DOSES AND THE DOSING REGIMEN

The dosing regimen combines both accelerated titration and standard cohort dose escalation schemata, which will be used jointly to identify the maximum tolerated dose (MTD) and recommended Phase 2 dose (RP2D) of BVD-523 in human patients.

The proposed human Phase 1 starting dose for BVD-523 is derived from 28-day GLP toxicology studies performed in rodent and non-rodent species and calculated as described in [Senderowicz 2010](#). Specifically, our results indicated that toxicity in rodents would be used to establish starting dose in patients. The severely toxic dose in 10% of the animals (STD10) for BVD-523 when administered for up to 28 days in Sprague-Dawley rats was determined to be 12.5 mg/kg dosed twice daily (25 mg/kg/day). A standard 10-fold reduction of this dose was scaled to establish a starting dose of 13.5 mg twice-daily of BVD-523 (free base equivalents) or 14.6 mg twice-daily of BVD-523, based on an average body surface area of 1.8 m^2.

Consistent with current clinical practice and dosing convenience, the proposed starting dose for the Phase 1 clinical study with BVD-523 in cancer patients is 10 mg twice-daily (20 mg/day).

Since there are no pre-clinical data to suggest that flat dosing will lead to greater inter-patient PK variability, flat milligram dosing without adjustment for body size will be used in this study ([Mathijssen 2007](#)). The effects of weight and body surface area on PK may be studied retrospectively as part of the PK analysis.

### 3 STUDY DESIGN

#### 3.1 STUDY DESIGN OVERVIEW

This is an open-label, multi-center Phase 1 study to assess the safety, pharmacokinetics, and pharmacodynamics of escalating doses of BVD-523 in patients with advanced malignancies. The study will be conducted at up to 15 sites.

##### 3.1.1 Study Objectives

###### 3.1.1.1 Primary Objective

To define the safety and tolerability of BVD-523 in patients with advanced malignancies by determining the dose-limiting toxicities (DLT), the maximum tolerated dose (MTD), and the recommended Phase 2 Dose (RP2D).

###### 3.1.1.2 Secondary Objectives

- To determine the pharmacokinetic profile of BVD-523 and selected metabolites in patients with advanced malignancies
- To investigate any preliminary clinical effects on tumor response assessed by physical or radiological exam (RECIST 1.1)

###### 3.1.1.3 Exploratory Objectives

- To evaluate pharmacodynamic marker (biomarker) measures

##### 3.1.2 Study Design

This clinical study comprises 2 parts:

- Part 1: Dose-escalation Phase
- Part 2: Cohort Expansion Phase

Part 1 – Dose-escalation Phase: An accelerated dose escalation plan will be used to establish dose limiting toxicities (DLT), maximum tolerated dose (MTD), and the recommended Phase 2 dose (RP2D). One to 6 patients per treatment cohort will be assigned to receive sequentially higher oral doses of BVD-523 on a twice daily schedule (b.i.d.) for 21 days (a “Cycle”), starting at a dose of 10 mg twice daily. Patients will receive twice-daily oral doses of BVD-523 until disease progression, unacceptable toxicity, or a clinical observation satisfying another withdrawal criterion is noted. Treatment cycles will occur consecutively without interruption, except when necessary to manage toxicities.

Patients with advanced-stage solid tumors only (no hematological malignancies) will be enrolled in the dose-escalation phase of the study. The study will initially be conducted as an accelerated single patient design, followed by a standard 3 + 3 design, informed by the

accrued safety experience throughout the study (see Table 3.2 below). All dose-escalation decisions will be based on Cycle 1 safety data.

In the accelerated single patient phase, 1 patient will be enrolled in a cohort and an evaluation of dose escalation will take place after the patient has completed the 21-day treatment cycle. If the patient exhibits no Grade 2 or greater adverse events, dose escalation in a 100% increment and enrollment will continue with a single patient per cohort. However, when one patient experiences a  $\geq$  Grade 2 toxicity (excluding alopecia or diarrhea), this cohort and subsequent cohorts will be expanded to at least 3 patients each following the classic 3 + 3 design and dose escalation increments will be reduced from 100% to a maximum of 50%, as determined by discussion with the Clinical Investigators, the Medical Monitor, and the Sponsor. Doses will not be escalated unless the patient(s) receiving the highest current dose has been observed for at least 3 weeks.

The classic 3 + 3 design will be conducted as follows. Initially, 3 patients will be enrolled to a cohort; the occurrence of a single drug-related DLT in one of these 3 patients will prompt enrollment of up to an additional 3 patients to that same cohort i.e., 3 + 3. When more than 1 DLT occurs in  $\leq$  6 patients in a dosing cohort, dose escalation will be stopped and this dose level will be identified as the non-tolerated dose. Doses between the non-tolerated dose and the preceding lower dose, where  $\leq$  1 DLT occurred, may be explored to define the MTD. This strategy allows for a rigorous determination of MTD, especially if the dose increase that resulted in determination of the non-tolerated dose is relatively large (i.e.,  $>$  50%).

At any time during the study, the Sponsor and Investigators may request that cohorts should be enlarged or that exploration of intermediate doses between 2 planned escalation steps should be explored. Such requests will be discussed with the Sponsor and Medical Monitor, and should be based on all data existing at that time, including determinations of pharmacokinetics, pharmacodynamics, and cumulative toxicity. Before each escalation, investigators will be consulted to ensure that all involved agree with the escalation decision.

In addition, once the RP2D is defined, intra-patient dose escalation to the RP2D will be allowed after a patient has completed at least 1 cycle at their assigned dose and only if the patient has experienced no toxicity above Grade 1, upon request by the PI and discussion with the Medical Monitor and the Sponsor.

Part 2 – Cohort-expansion Phase: Additional patients with particular tumor types and/or cancers harboring specific genetics will be recruited for treatment at the Recommended Phase 2 Dose (RP2D). Patients must have measurable disease by RECIST 1.1. Patients will receive twice daily oral doses of BVD-523 in 21-day treatment cycles until disease progression, unacceptable toxicity, or another withdrawal criterion is met (Section 7.2). Treatment cycles will occur consecutively without interruption except when necessary to manage toxicities.

Total enrollment for Part 2 is targeted at approximately 105 evaluable patients. Patients will be enrolled into 1 of 7 treatment groups. Group assignments are made according to the following disease characteristics, which correspond to specific inclusion and exclusion criteria for Part 2.

- Group 1: Patients with BRAF mutated cancer, except those with colorectal or non-small cell lung cancers, not previously treated with BRAF and/or MEK inhibitors; n ≤ 15
- Group 2: Patients with BRAF mutated colorectal cancer, not previously treated with BRAF and/or MEK inhibitors; n ≤ 15
- Group 3: Patients with BRAF mutated melanoma who have progressed or are refractory to BRAF and/or MEK inhibitors; n ≤ 15
- Group 4: Patients with NRAS mutated melanoma, not previously treated with BRAF and/or MEK inhibitors; n ≤ 15
- Group 5: Patients with MEK mutated cancer, not previously treated with BRAF and/or MEK inhibitors; n ≤ 15
- Group 6: Patients with BRAF mutated non-small cell lung cancer, not previously treated with BRAF and/or MEK inhibitors; n ≤ 15
- Group 7: Patients with ERK mutated cancer, not previously treated with BRAF and/or MEK inhibitors; n ≤ 15

Initial enrollment targets for each group may be modified to respond to accrued safety, clinical effect, pharmacokinetic, and pharmacodynamic data. The decision to expand enrollment in one or more groups will be made through consultation among the Principal Investigators, the Medical Monitor and the Sponsor.

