### **4.2 RECRUITMENT**

Three to 10 study centers will enroll up to 40 patients for Part 1.

In addition to the sites supporting Part 1 studies, sites may be added (up to 15 total sites) to enroll up to approximately 105 evaluable patients for Part 2 of the study.

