4 SAMPLE SIZE CONSIDERATIONS

For this Phase 1 dose escalation study, no formal sample size calculations have been performed; the sample size reflects practical considerations.

Approximately 40 patients will be treated in Part 1 of this study (dose-escalation phase) to establish DLT, MTD, and the RP2D.

After the completion of Part 1 of this study, up to 105 additional patients with certain cancer types and/or characterized genetic alterations and/or MAPK pathway activation will be treated with the RP2D (which may be the same or lower than the MTD) to determine if BVD-523 is effective as a single agent therapy. The purpose of the second phase of this first in human research is to merely document that there is some evidence of a response (complete response or partial response per RECIST v 1.1).

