9 EFFICACY ANALYSIS

Unless otherwise stated, efficacy analyses will be performed on both the mITT and PP populations (see Section 5 of this SAP).

Tumor measurements based on physical examination will occur at baseline and on the first day of each treatment cycle. Tumor assessments will be made by CT/MRI/Physical Exam prior to dose initiation, at the first protocol-specified tumor measurement evaluation at the end of Cycle 2 and then every 2-3 cycles, and at End of Treatment.

In Part 1, FDG-PET scans were performed at investigator discretion based on totality of additional available data for the subject.

RECIST

Imaging will be performed on the abdomen, chest, pelvis and the site of the primary tumor if elsewhere. The same imaging modality used for an individual patient (i.e., CT or MRI) at Screening should be maintained throughout the study. The findings will be assessed according to the Response Evaluation Criteria in Solid Tumors (RECIST version 1.1).

The response criteria in evaluation of target lesions are defined as follows:

- Complete Response (CR): Disappearance of all target lesions. Any pathological lymph nodes (whether target or non-target) must have reduction in short axis to < 10 mm.
- Partial Response (PR): At least a 30% decrease in the sum of diameters of target lesions, taking as reference the baseline sum diameters.
- Progressive Disease (PD): At least a 20% increase in the sum of diameters of target lesions, taking as reference the smallest sum on study (this includes the baseline sum if that is the smallest on study). In addition to the relative increase of 20%, the sum must also demonstrate an absolute increase of at least 5 mm. (Note: the appearance of 1 or more new lesions is also considered progression).
- Stable Disease (SD): Neither sufficient shrinkage to qualify for PR nor sufficient increase to qualify for PD, taking as reference the smallest sum diameters while on study.

The number and percent of patients with each tumor response will be tabulated using the PP Population by study part, dose level/treatment group, and study visit. Bar graphs of genetic information (BRAF, FGFR3, etc.) leading to target lesion response and best overall response will also be presented.

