12 INTERIM ANALYSIS

Once all subjects enrolled into Part 1 of the study have been assessed for at least one full treatment cycle, an analysis of Part 1 safety and efficacy will be conducted in order to facilitate the discussions regarding MTD and RP2D; however, no formal interim analysis is planned for the study.

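### A Part 2 group may be enlarged because of its observed responses, but the SAP does not separate patients enrolled before and after that decision, so the reported rate keeps part of the selection bias

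*Protocol*

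**What the plan says.** Part 2 enrolls into seven groups defined by tumor type and mutation, each with a size of the form "Patients with BRAF mutated colorectal cancer, not previously treated with BRAF and/or MEK inhibitors; n ≤ 15" (protocol 3.1.2, Group 2). The same section then says: "Initial enrollment targets for each group may be modified to respond to accrued safety, clinical effect, pharmacokinetic, and pharmacodynamic data". On procedure it says: "The decision to expand enrollment in one or more groups will be made through consultation", the parties being the principal investigators, the medical monitor and the sponsor. The study is open-label, so all of them can see responses as they accrue. Neither document gives a look time, a response threshold or an upper limit for an enlarged group.

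On analysis, SAP 9 says: "The number and percent of patients with each tumor response will be tabulated using the PP Population by study part", and further by dose level or treatment group and by visit. The Part II efficacy displays listed in SAP 14 (Tables 14.2.1 to 14.2.8 and their figures) name no split by stage of enrollment. The shells themselves are separate documents that are not available here. SAP 12 describes an early analysis of Part 1 only and adds that "no formal interim analysis is planned for the study". SAP 15 records that this version was revised for amendments 5 to 7 and for the Part 2 displays, yet the SAP nowhere mentions enlarging a group.

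**The concern.** If early responses help decide that a group grows, the patients who prompted the decision are a favorable sample of that group by construction. Those added later are not. One percentage over both sets sits above the true rate on average, and the groups left at their initial size sit below it, even if all seven groups respond equally.

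This matters because estimates are the whole efficacy output of Part 2. No test is planned (SAP 6.5), no multiplicity adjustment is made (SAP 6.4), and no confidence interval for response is specified. The seven groups are the only planned subgroups (SAP 6.3). A reader will compare bare percentages across groups and will not know which were enlarged on their results.

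**Working it through.** **The plan's own figure.** Protocol 4.1 and 10.1.2 give an 80% chance of at least one response in 15 patients at a true rate of 10%. 1 − 0.9^15 = 0.794, so the figure reproduces.

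**Assumptions.** The documents give no expansion rule. I assume one look at n1 = 15 patients, expansion if the number of responders X is at least k, and n2 = 15 patients added, with X ~ Bin(15, p). The value p = 10% comes from the protocol's sample-size statement; p = 5% and 20% are sensitivity values.

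**Formulas.**
- Initial patients in enlarged groups: E[X | X ≥ k] / 15
- Combined: (E[X | X ≥ k] + n2·p) / (15 + n2)
- Added patients alone: p, since they play no part in the decision

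**p = 10%, k = 2.** P(X=0) = 0.2059 and P(X=1) = 0.3432, so P(X≥2) = 0.451. E[X | X≥2] = (1.5 − 0.3432)/0.451 = 2.565. Initial: 2.565/15 = 17.1%. Combined: (2.565 + 1.5)/30 = 13.6%.

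**p = 10%, k = 3.** P(X=2) = 0.2669, so P(X≥3) = 0.184. E[X | X≥3] = (1.5 − 0.3432 − 2 × 0.2669)/0.184 = 3.385. Initial: 22.6%. Combined: (3.385 + 1.5)/30 = 16.3%.

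**p = 5%, k = 2.** P(X=1) = 0.3658 and P(X≥2) = 0.171. E[X | X≥2] = (0.75 − 0.3658)/0.171 = 2.248. Initial: 15.0%. Combined: (2.248 + 0.75)/30 = 10.0%.

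| True rate | Trigger | Chance a group expands | Initial 15 | Combined 30 | Added 15 |
|---|---|---|---|---|---|
| 10% | ≥2 | 45% | 17.1% | 13.6% | 10% |
| 10% | ≥3 | 18% | 22.6% | 16.3% | 10% |
| 5% | ≥2 | 17% | 15.0% | 10.0% | 5% |

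**Range over other assumed rules.** With 15 added and triggers from 1 to 4, the excess of the combined rate is 1.3 to 9.3 points at a true 10%, 2.2 to 11.2 at 5% and 0.4 to 5.7 at 20%. With only 5 added at a true 10%, it is 1.9 to 13.9 points.

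**Is a chance trigger plausible?** With seven groups all at 10%, the probability that at least one shows 3 or more responders in 15 is 1 − (1 − 0.184)^7 = 76%.

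**Where the bias comes from.** At a true 10% with a trigger of 3, groups below the trigger average 7.2%. The gap between selected and unselected groups is 22.6 − 7.2 = 15.4 points before anyone is added and 16.3 − 7.2 = 9.1 points after expansion and combination. Similarly, with seven equal groups at 10%, simulation puts the best group at 21.2% on 15 patients and 15.6% after 15 more are added and combined.

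**The case against.** The strongest reply is that the protocol claims little for these rates. Response is a secondary endpoint, protocol 10.3.6 rules out a formal efficacy analysis, SAP 5.3 calls per-protocol results exploratory, and SAP 4 limits the aim of Part 2 to showing that responses occur. Whether a responder was seen is not biased by combining patients. No ranking of groups and no go/no-go threshold is planned. All of this stands, and it keeps the point to one of reporting.

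The figures are also conditional on expansion. Averaged over enlarged and unenlarged groups, the reported rate is slightly low: 8.4% (trigger 2) and 8.8% (trigger 3) at a true 10%, and 4.1% at a true 5% (trigger 2). That stands too, but a reader looks at the enlarged group, not at the average. Protocol 3.1.2 also lists safety, pharmacokinetic and pharmacodynamic data as grounds, so a change need not be driven by response.

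Three stronger readings are tempting, and none is supported.

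- A reader might infer that expansion creates the bias. It does not: selection on early results does, and new patients shrink it.
- A reader might infer that expansion breaks the stated caps, since 7 × 15 = 105. But 3.1.2 itself calls the group sizes initial targets that may be modified, and "Total enrollment for Part 2 is targeted at approximately 105 evaluable patients". One group of 30 fits within 105 if the other six total no more than 75. What remains is editorial: protocol 4.2 says "up to approximately 105 evaluable patients for Part 2 of the study" and SAP 4 says "up to 105 additional patients with certain cancer types", neither mentioning expansion.
- A reader might infer that only the added patients should count. Their rate is unbiased but less precise. With 15 + 15 patients, root mean squared error in enlarged groups is 5.9 points combined against 7.7 added-only (10%, trigger 2), 7.7 against 7.7 (10%, trigger 3), and 6.0 against 5.6 (5%, trigger 2). Neither estimate wins throughout.

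**Conclusion.** The point holds as a limited one about reporting. Followed as written, the plan gives a single rate per group that is too high on average in any group enlarged because it responded. Under a look at 15 with 15 added, the excess is 3.6 points (trigger 2) or 6.3 points (trigger 3) at a true 10%, and 5.0 points at a true 5% (trigger 2), where the combined rate is double the truth. Look time, trigger and number added are all assumptions. With fewer patients added the excess is larger; with a lower trigger or a higher true rate it is smaller. No type I error or success criterion is at stake. What the current tables lack is a view of the patients whose responses played no part in the decision.

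**What to change.** In SAP 9, add a rule for any Part 2 group expanded after response data were seen: record the date of the decision, and tabulate initial, added and combined patients side by side, each with an exact 95% confidence interval. A footnote should say that the initial and combined rates are subject to selection and the added-patient rate is not. The added-patient rate should not be the only estimate reported.

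The cost is one extra table split, a dated record and wide intervals for the added patients: 1 responder in 5, for example, has an exact 95% interval of 0.5% to 72%. The patient-level response listings already planned for Part II can support the split once the date is recorded. Enrollment, eligibility and the sponsor's freedom to expand a group are unchanged.

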**Table 3.1. Study Medication Dosing and Pharmacokinetics/Pharmacodynamics Chart**

	Study Days			
	1	8	15	22
BVD-523 Dosing 	X	X	X	X
Pharmacokinetics Sampling	X		X	X
Pharmacodynamics Sampling 	X		X	

 Dosing is twice daily in 21-day cycles until disease progression. Patients may be treated beyond disease progression for additional 21-day cycles at the same dose level at the Investigator’s discretion. However it is particularly important in patients for which FDA approved BRAF and/or MEK inhibitors are indicated that BVD-523 treatment NOT be continued beyond tumor progression. Study medication for a week of dosing will be dispensed at each visit (± 1 day for Cycles 1 and 2, ± 2 days for later cycles). For treatment cycles after Cycle 2, study medication for 3 weeks of dosing will be dispensed. Additional medication may be dispensed to ensure uninterrupted dosing, if needed.

 Pharmacodynamic sampling should only be completed in those patients that consent to optional biopsy. Those patients that do not consent to this collection do not need to have pharmacodynamics samples taken.

### 3.1.3 Summary of Dose Escalation

**Table 3.2. Summary of Dose Escalation**

Observed Safety Outcomes	Action
Single Patient Cohorts	
AEs $\leq$ Gr 1	
 
Continue testing with single patient cohorts
 
Escalate by 100% to next dose level
 

One AE $\geq$ Gr 2 (excluding alopecia or diarrhea)	
 
Expand current and subsequent cohorts to <math>\geq</math> 3 patients
 
Escalate by <math>\leq</math> 50% to next dose level
 

1 DLT	
 
Expand cohort up to 6 patients
 

Standard Escalation Cohorts (3–6 patients)	
No DLTs	
 
Escalate by <math>\leq</math> 50% to next dose level
 

1 DLT in 3 patients	
 
Expand cohort up to 6 patients
 

1 DLT in 6 patients	
 
Escalate by <math>\leq</math> 50% to next dose level
 

> 1 DLT in $\leq$ 6 patients	
 
Stop dose escalation
 

*Note:* DLT (see Section 3.1.4.2) is defined as any BVD-523 related toxicity in the first 21 days of treatment that results in:

- $\geq$  Grade 4 hematologic toxicity for > 1 day
- Grade 3 hematologic toxicity with complications e.g., thrombocytopenia with bleeding
- $\geq$  Grade 3 non-hematologic toxicity, except untreated nausea, vomiting, constipation, pain and rash (these become DLTs if the AE persists despite adequate treatment), a doubling of AST/ALT in patients with grade 2 ALT/AST at baseline
- A treatment interruption exceeding 5 days (or an interruption exceeding 7 days for rash, despite adequate treatment) in Cycle 1 (or inability to begin Cycle 2 for > 7 days) due to BVD-523-related toxicity.

Each cohort can only begin when the previous cohort has completed treatment to at least the end of Week 3 without fulfilling a criterion that would prevent dose escalation.

Although dose escalation decisions may be taken upon review of the data from Cycle 1, safety data will be collected from all patients continuing treatment and reviewed periodically by the Safety Monitoring Committee. Any detected cumulative toxicity may require later dose reductions or other action as appropriate, including having an effect on the RP2D.

